##### **Complete Response + Complete Response with incomplete recovery rate**

In the Phase 2 portion of this study the primary end point will be the CR +CRI rate as determined using IWG criteria. The response status of each patient will be determined prior to each cycle of DACOGEN + cytarabine after the first cycle. The best response up to 4 cycles of DACOGEN + cytarabine for each subject will be used to determine the rate of CR + CRI.

To be evaluable, subjects must complete at least 2 cycles of the sequential retreatment and have at least 1 post baseline disease assessment unless disease progression or response (CR, CRI, or PR) occur prior to the planned disease assessment but after Cycle 1 treatment (ie, after Day 13 of Cycle 1).

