## EFFICACY EVALUATIONS/ENDPOINTS

Efficacy evaluations will be performed on Day 28 of each cycle or within 8 days of the start of the next cycle. Response will be assessed using International Working Group (IWG) criteria. The best response from up to 4 cycles of sequential treatment for each subject in the Phase 2 portion of the study will be used to determine the primary endpoint, response rate of CR + CRI. To be evaluable, subjects must complete at least 2 cycles of the sequential treatment and have at least 1 post-baseline disease assessment unless subjects discontinued treatment before Cycle 2 with disease progression or response (CR, CRI, or PR). Other efficacy endpoints include duration of response for subjects who achieve CR, CRI, overall response rate (CR + CRI + PR), OS, and EFS.

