## STATISTICAL METHODS

The safety population comprises subjects who signed the informed consent form (ICF) and received at least 1 dose of any study drug. The efficacy population is the subset of the safety population consisting of subjects who are evaluable for disease response. Subjects who withdraw prior to the completion of 2 cycles for reasons other than disease progression or response (CR, CRI, or partial response [PR]) and do not have at least 1 post-baseline disease assessment will be considered non-evaluable for response. Where appropriate, summaries (demographic, baseline characteristics, efficacy, and safety) will be presented for the Phase 1 part of the data, the Phase 2 part of the data, and data of the 2 phases combined.

The Phase 1 portion of the study will enroll up to 18 evaluable subjects (if the intermediate cytarabine dose is used), depending on when the MTD is determined. The Phase 2 portion of this study will include at least 15 evaluable subjects and is aimed to provide initial efficacy and additional safety data for the sequential administration of DACOGEN and cytarabine.

The primary efficacy endpoint is the response rate of CR + CRI for evaluable subjects from the Phase 2 part of the study. Statistical analyses include the percent of subjects who achieve a CR or CRI and the 95% confidence interval. The analyses are descriptive with the aim of assisting decision making for further clinical development of the sequential combination therapy. The best response observed at any time point during the 4 cycles of study treatment will be used. The response rate for subjects from the Phase 1 part of the study, and from Phase 1 and Phase 2 parts combined will also be summarized.

Duration of CR + CRI, overall response rate (CR + CRI + PR), event-free survival, and overall survival will be summarized. These summaries are also based on data of the Phase 2 part of the study. Where appropriate, these summaries will be performed on data from the Phase 1 part of the study and Phase 1 and Phase 2 parts combined.

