### **10.2. Discontinuation of Study Treatment (Sequential DACOGEN - cytarabine)**

If a subject's study treatment must be discontinued, the End of Sequential Treatment Visit should be performed however, this will not result in automatic withdrawal of the subject from the study. The subject may, at the discretion of the investigator, receive single agent DACOGEN in the Continuation Phase (see Section 9.1.5), otherwise the subject will enter the Follow-up Phase of the study. The End of Sequential Treatment/End of Treatment Visit and Follow-up visit assessments should be performed as specified in the Time and Events Schedule.

A subject's study treatment should be discontinued if:

- The subject experiences a DLT in the Phase 1 portion of the study
- The investigator believes that for safety reasons (eg, adverse event) it is in the best interest of the subject to discontinue study treatment
- The subject becomes pregnant
- The subject has progressive disease by IWG criteria
- The subject is non-compliant with regard to treatment visits
- The subject has sufficient clinical response, in the opinion of the investigator, to be eligible for transplant

- The subject starts another treatment regimen for AML
- The subject is unable to adhere to the study visit schedule or comply with protocol requirements
- The subject or subject's legal representative, parent, or guardian withdraws consent/assent for study treatment.

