### **11.1. Subject Information**

The safety population includes subjects who have signed the ICF and have received at least 1 dose of any study drug. The efficacy population is the subset of the safety population consisting subjects who are evaluable for disease response. Where appropriate, summaries (demographic, baseline characteristics, efficacy, and safety) will be presented for Phase 1 part of the data, Phase 2 part of the data, and data of the 2 phases combined.

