### 11.4. Efficacy Analyses

#### Criteria

##### *Primary Endpoint*

The primary efficacy endpoint is the response rate of CR + CRi for evaluable subjects from the Phase 2 part of the study. The best response observed at any time point during the first 4 cycles of study treatment will be used.

Best response of CR + CRi for subjects from the Phase 1 part of the study, and from Phase 1 and Phase 2 parts combined will also be summarized.

The aim of the statistical analysis of the initial efficacy data is to assist decision making for further clinical development of DACOGEN sequential therapy. Such a decision will be in consultation with regulatory authorities, and will depend primarily on the totality of the data from this and other studies, available treatment options for pediatric AML patients at the time, and interest of co-operative study groups.

The sequential therapy is considered not to have a clinically interesting activity if the underlying response rate (CR + CRi) is  $\leq 20\%$ , and is considered to have a clinically interesting activity if the underlying response rate is  $\geq 35\%$ . Because of the small sample size (15 subjects), only descriptive statistics, ie, the observed response rate of CR + CRi and the 95% confidence interval (CI), will be provided without any hypothesis testing. Also, due to the small sample size, the observed response rate will have much variability. With these considerations, descriptive statistical analyses will focus on 2 assessments that are considered adequate and reasonable in the context of small sample sizes.

The first analysis is to use the lower boundary of the 95% CI to assess if an underlying response rate that is much smaller than 20% can be ruled out. For instance ([Table 5](#)), with a total of 15 subjects, to rule out an underlying response rate of 5%, there should be at least 4 responders, and to rule out an underlying response rate of 3%, there should be at least 3 responders.

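### Two incompatible evaluability rules for the primary CR + CRi rate: a child who stops early with a disease assessment but no response or progression is dropped under 9.2.2 and kept under the Synopsis statistical text

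*Combined protocol and SAP*

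**What the plan says.** The protocol body defines evaluability for response once, in 9.2.2 under the Phase 2 primary endpoint: "To be evaluable, subjects must complete at least 2 cycles of the sequential retreatment and have at least 1 post baseline disease assessment". The exception is progression or response (CR, CRi or PR) before the planned assessment, "but after Cycle 1 treatment (ie, after Day 13 of Cycle 1").

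The Synopsis, under Efficacy Evaluations/Endpoints, has the same two-part requirement: "To be evaluable, subjects must complete at least 2 cycles of the sequential treatment and have at least 1 post-baseline disease assessment". It exempts children who left treatment before Cycle 2 with progression or response, and sets no Day 13 limit.

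The Synopsis, under Statistical Methods, works by exclusion. Subjects who withdraw before completing 2 cycles for reasons other than progression or response, and who "do not have at least 1 post-baseline disease assessment will be considered non-evaluable for response".

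The analysis sections rely on the term without defining it. Section 11.1: "The efficacy population is the subset of the safety population consisting subjects who are evaluable for disease response". Section 11.4: "The primary efficacy endpoint is the response rate of CR + CRi for evaluable subjects from the Phase 2 part of the study". Neither points to a definition. Section 11 leaves details to a Statistical Analysis Plan, and no text in the document provided settles the question.

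**The concern.** The primary endpoint is a proportion in about 15 children, so one or two children in or out of the denominator is visible. The disputed child can arise. A marrow is scheduled at the end of Cycle 1 and at the End of Sequential Treatment Visit (9.2.1). Section 10.2 lists reasons to stop that are neither response nor progression, including adverse events, withdrawn consent and "The subject starts another treatment regimen for AML".

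The effect has one direction. A child who responds early is exempt from the 2-cycle requirement; a child who stops early without responding is not, unless the disease progressed. The 9.2.2 rule therefore removes non-responders and never responders on this route. In an open-label, single-arm study, the denominator rule should not be left to be chosen once outcomes are known.

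At stake are the observed CR + CRi rate and the way Table 5 is read. Section 11.4 presents that table's error rates as one of two assessments to help decide on further development.

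**Working it through.** **Step 1. The rules applied to the same children.**

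| Child | 9.2.2 and Synopsis efficacy text | Synopsis statistical text |
|---|---|---|
| Stops before 2 cycles, no response or progression, has an assessment | Out | In, as a non-responder |
| Same, but no assessment | Out | Out |
| Stops before 2 cycles with progression or response | In (9.2.2: only after Day 13 of Cycle 1) | In |
| Completes 2 cycles, no assessment, no documented progression or response | Out | Not excluded |

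Row 1 is the main conflict. Row 3 shows the Day 13 difference. Row 4 is a conflict the other way, and 9.2.1 gives a response rule without marrow only from 3 cycles.

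**Step 2. Inputs.** At least 15 evaluable and an estimated 17 enrolled in Phase 2 (11.2), so an allowance of 17 − 15 = 2 for all causes of non-evaluability. Reference rates are 20% and 35%, with Clopper-Pearson intervals (11.4, Table 5). The documents do not say how many children would fall in row 1; 0, 1 or 2 is an assumption.

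**Step 3. Reproduce Table 5 (n = 15).** The false positive figure is P(X ≥ x) for X ~ Binomial(15, 0.20). For x = 5: 1 − 0.8358 = 16.4%. The false negative figure is P(X ≤ x) for X ~ Binomial(15, 0.35). For x = 4: 35.2%. All seven rows match as printed.

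**Step 4. Remove only non-responders.** Treat N children and drop k non-responders to leave N − k = 15. The responder count is unchanged, so it still follows Binomial(N, p), not Binomial(15, p). For at least 5 responders at p = 0.20: N = 16 gives 1 − 0.7982 = 20.2%; N = 17 gives 1 − 0.7582 = 24.2%.

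| Responders | Rate, % (n = 15 / 16 / 17) | P(≥ x) at 20%, % (15 / 16 / 17) | P(≤ x) at 35%, % (15 / 16 / 17) |
|---|---|---|---|
| 3 | 20.0 / 18.8 / 17.6 | 60.2 / 64.8 / 69.0 | 17.3 / 13.4 / 10.3 |
| 4 | 26.7 / 25.0 / 23.5 | 35.2 / 40.2 / 45.1 | 35.2 / 28.9 / 23.5 |
| 5 | 33.3 / 31.3 / 29.4 | 16.4 / 20.2 / 24.2 | 56.4 / 49.0 / 42.0 |
| 6 | 40.0 / 37.5 / 35.3 | 6.1 / 8.2 / 10.6 | 75.5 / 68.8 / 61.9 |

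With 5 responders the observed rate moves by 33.33 − 31.25 = 2.1 points, or 33.33 − 29.41 = 3.9 points.

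**Step 5. Does a fixed N matter?** Suppose instead that recruitment runs until 15 are evaluable and a fraction q of treated children is dropped this way. The rate among evaluable children is then 0.20/(1 − q). With q = 1/16 this is 21.3%, and with q = 2/17 it is 22.7%. P(X ≥ 5) for n = 15 is 20.0% or 23.9%, close to Step 4.

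**Step 6. Lower-bound assessment.** The lower 95% limit for 4 responders is 7.8%, 7.3% and 6.8% with n = 15, 16 and 17; for 3 responders it is 4.3%, 4.0% and 3.8%. So 4 responders still rule out 5%, and 3 still rule out 3%.

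**The case against.** The strongest reply is that the question is less open than it looks. Section 9.2.2 is the only definition in the protocol body, and the Synopsis efficacy text repeats it. The outlier is one Synopsis sentence, whose *and* may be loose drafting for *or*. A separate Statistical Analysis Plan might also settle it. This largely stands: a reader might infer that the plan leaves the denominator undefined, and the documents do not support that. They do contain two conflicting statements, and 9.2.2, the better placed, is the one that drops non-responders.

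A reader might also infer that any child with a dose-limiting toxicity at the MTD falls into the gap. Section 10.2 does list "The subject experiences a DLT in the Phase 1 portion of the study" as a reason to stop, Table 3 allows 1 such child among 6 at the declared MTD, and 3.1.2 brings evaluable MTD children into Phase 2. But 9.5 assesses hematological toxicity only in responding patients without leukemia, and 9.2.2 excludes malignant infiltration. A formal CR, CRi or PR meets the response exception. What remains is mainly non-hematological toxicity without response.

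Other routes are narrow too. Investigator judgment can establish progression (9.2.1), which makes the child evaluable under both rules, subject to the Day 13 limit in 9.2.2. A child who leaves with no assessment is excluded under both.

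Finally, 24.2% might be taken as the true false positive rate. It is a ceiling: it sends both spare children down this one route and applies the 20% rate per treated child. If 20% refers to evaluable children, as the endpoint wording allows, 16.4% stands.

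**Conclusion.** The inconsistency is real and affects the primary denominator. Relative to keeping the early-stopping child, the 9.2.2 rule can only raise the CR + CRi rate or leave it at 0%; that follows from the wording and needs no assumption about numbers.

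The size is modest and uncertain, and may be zero. If 1 or 2 non-responders are removed to leave 15, the observed rate with 5 responders rises by 2.1 or 3.9 points. That is small against the interval of 11.8% to 61.6% at 5/15. If the reference rates also apply per treated child, the chance of at least 5 responders at a true 20% is 20.2% or 24.2% instead of 16.4%, and the chance of 4 or fewer at a true 35% is 28.9% or 23.5% instead of 35.2%.

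A reader might infer that Table 5 is miscalculated. It is not: every row is correct for 15 children taken without regard to outcome. No hypothesis test is affected, since the analysis is descriptive, and 11.4 rests the development decision mainly on the totality of the data. The point is still worth correcting because the direction is known and the correction is cheap.

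**What to change.** Use one rule in 9.2.2, in 11.4 and in both Synopsis texts:

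*A treated subject with at least 1 post-baseline disease assessment, or with documented progression or response, is evaluable; one who has not achieved CR or CRi is a non-responder, whatever the reason for stopping. Subjects with no post-baseline disease assessment and no documented progression or response are non-evaluable.*

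This settles the early-stopping child, and also the child who completes 2 cycles without any assessment or documented outcome, who becomes non-evaluable.

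State whether the Day 13 limit is kept, and word all four places alike. Without it, a child who progresses before receiving any cytarabine (given on Days 8 to 12) counts as a failure of the sequence. With it, the progression clause above needs the same qualifier.

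As a sensitivity row, report CR + CRi in all treated Phase 2 subjects, including Phase 1 subjects treated at the MTD.

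The cost is wording and one descriptive row, with no added subjects or visits. The reported rate may be slightly lower. Some children counted as non-responders will have had only one cycle, although response can come later: section 3.2 cites a median of 2.5 cycles to best response in the pediatric single-agent data.

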## Secondary Endpoints

- Safety profile of DACOGEN 20 mg/m^2 per day on Days 1-5 followed by cytarabine Days 8-12 for up to 4 cycles of therapy.
- Duration of CR + CRi
- Overall response (CR + CRi + PR)
- Event-free survival (EFS), defined as the time from first dose of study drug to relapse from CR, death, or second malignancy for subjects who achieve CR; subjects who do not achieve CR will be considered to have an event on the day of the first dose of study drug. Other alternative EFS definitions may be considered.
- Overall survival
- To determine the PK profile of DACOGEN in children with AML

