**Figure 3: Schematic Overview of the Study**

### 3.2. Study Design Rationale

#### Rationale for Sequential Therapy

The addition of a new agent to available regimens can mediate their clinical benefit on the premise that the combined agents have non-overlapping and synergistic mechanisms of action.

Cytarabine is a core component of initial and later therapy for patients with AML regardless of patient age. AML treatment guidelines indicate that therapy should combine an anthracycline with standard-dose cytarabine with or without other agents, high-dose cytarabine alone or combined with an anthracycline, asparaginase or etoposide or using the purine analogues, fludarabine or 2 chloro-deoxyadenosine combined with high-dose cytarabine, with or without an anthracycline and/or granulocyte-colony stimulating factor.

The recent demonstration of a role for low dose DACOGEN for the treatment of older patients with AML creates the opportunity to explore the potential benefit of DACOGEN in younger age groups. Limited data available from small clinical trials suggest that DACOGEN is active in pediatric patients with AML:

- Preliminary single agent Phase 2 data in very high risk relapsed pediatric AML patients showed that DACOGEN administered as a 20 mg/m^2 IV infusion on Days 1-10 (Q 28 days) produced antileukemic effects. Of 8 subjects treated (ages 2-26, median age 4 years) with DACOGEN, 3 subjects had a CR, complete remission with incomplete platelet recovery (CRp) or CRI, 3 subjects had a PR, 1 had stable disease and 1 had progressive disease. Median time to best response was 2.5 cycles and the drug was well tolerated with neutropenia as the most common toxicity with 2 serious infections in 24 cycles.
- A Children's Oncology Group (COG) study enrolled 2 patients with relapsed or refractory AML (N=2) and acute lymphocytic leukemia (ALL; N=8) between 2002 and 2005. The starting dose of DACOGEN was 10 mg/m^2 daily on Days 1-5 and 8-12 of a 28-day cycle. The study was closed early due to poor accrual and lack of effect. (personal communication, [name], Stanford University, Stanford, CA, USA)

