### Remission and Disease Progression/Relapse

The assessment of a response (CR or CRi), may be made only when laboratory findings meet specific criteria as defined by IWG. The timing of bone marrow assessments for efficacy endpoints will be driven by peripheral blast counts. Clinical judgment based on blood cell count recovery will dictate the exact time in each cycle when bone marrow aspirates should be taken.

Some patients may develop a relapse that leads to death quickly without having the possibility to evaluate formally the relapse of disease. Efforts should be made to obtain an autopsy report in such patients.

The dates of CR, CRi, PR, progressive disease, or any subsequent disease relapse after a response should be recorded. This should be based on the acceptable laboratory evidence from a bone marrow aspirate.

Details of the IWG criteria are given below:

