## Complete Remission

For the following 2 CR categories, extramedullary leukemia, such as CNS or soft tissue involvement, must be absent. There is no stated duration of response required for a subject to be classified as a complete responder.

- **Morphologic Complete Remission (CR)**

Per the IWG criteria, CR is defined as morphologic leukemia-free state, with less than 5% blasts in aspirate sample with marrow spicules and with a count of  $\geq 200$  nucleated cells (there should be no blasts with Auer rods or any persistence of extramedullary disease), **plus** ANC  $> 1,000/\mu\text{L}$  platelet count of  $> 100,000/\mu\text{L}$  and subject must be independent of transfusions for a minimum of 1 week before each marrow assessment. No duration of response is required for CR.

- **Morphologic Complete Remission with incomplete blood count recovery (CRi)**

Per the IWG criteria, CRi is defined as morphologic CR with residual neutropenia ( $< 1,000/\mu\text{L}$ ) or thrombocytopenia  $< 100,000/\mu\text{L}$ ). No stated duration of response is required for CRi.

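### Does the EFS rule wrongly fail CRi-only responders on day 0 when the primary endpoint counts them as successes?

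*Combined protocol and SAP*

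**What the plan says.** Section 9.2.2 (Secondary Endpoints) starts EFS at the first dose. For subjects who reach CR it ends at relapse after CR, a second cancer or death. For the others, "subjects who do not achieve CR will be considered to have an event on the day of the first dose of study drug". The same bullet ends: "Other alternative EFS definitions may be considered". Section 11.4 (Major Secondary Endpoints) says that EFS will be summarised and repeats the start date; it adds no event rule.

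Elsewhere response is broader. Section 11.4 states: "The primary efficacy endpoint is the response rate of CR + CRi for evaluable subjects from the Phase 2 part of the study". The Synopsis lists response duration in the same terms: "Other efficacy endpoints include duration of response for subjects who achieve CR, CRI". In the Section 9.2.2 list itself, the bullets on response duration and overall response name CRi explicitly.

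Section 9.2.1 (Complete Remission) defines CR and CRi as separate entries with different blood-count requirements, under one introduction: "For the following 2 CR categories, extramedullary leukemia, such as CNS or soft tissue involvement, must be absent". It also requires that "The dates of CR, CRi, PR, progressive disease, or any subsequent disease relapse after a response should be recorded".

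Section 11 leaves further detail to a Statistical Analysis Plan. No separate text of that plan on EFS is among the documents reviewed.

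**The concern.** A subject whose marrow clears but whose neutrophils or platelets stay low is a success in the primary endpoint and has a response duration, yet on the literal EFS rule failed on the day of first dose. A reader of the study report could find these results hard to square. In an open-label single-arm study of about 15 evaluable subjects, moving one or two of them between time zero and a real follow-up time visibly shifts the curve. The open clause on alternative definitions adds to the worry: if the version to be shown is settled only after the CR and CRi outcomes are known, it could be picked for its appearance. At stake is the reading of a descriptive EFS curve, not the primary result.

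**Working it through.** **Inputs.** At least 15 evaluable Phase 2 subjects, with 17 planned to allow for non-evaluable ones (Section 11.2). Reference response rates of 20% and 35% (Section 11.4). Table 5 for N = 15. The documents give no CRi-only share; the earlier paediatric data in Section 3.2 pool the categories ("3 subjects had a CR, complete remission with incomplete platelet recovery (CRp) or CRI"). Any share used below is an assumption.

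**1. The plan's own figures.** With X binomial on 15 subjects, P(X ≥ x) at 20%, P(X ≤ x) at 35% and the Clopper-Pearson interval reproduce all seven rows of Table 5 to one decimal. For 5 responders: 33.3%, interval 11.8 to 61.6, errors 16.4% and 56.4%. For 7 responders: errors 1.8% and 88.7%. The EFS rule enters none of these.

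**2. Effect per subject.** Just after day 0, the proportion event-free is (number with CR)/15 under the literal rule and (number with CR or CRi)/15 under a broader one. Each CRi-only responder makes a difference of 1/15 = 6.7 points, or 1/17 = 5.9 points if all 17 planned subjects are the denominator. These figures are exact at day 0; later events and censoring alter them.

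Example with 5 of 15 responding and k of them CRi-only. Day-0 failures are (10 + k)/15 under CR-only: 66.7%, 73.3% and 80.0% for k = 0, 1, 2. Under CR + CRi they stay at 10/15 = 66.7%.

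**3. How often it would arise.** Let q = response rate × CRi-only share. The expected number is 15q and the chance of at least one is 1 − (1 − q)^15.

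| Assumed CRi-only share | Rate 20%: q, expected, chance | Rate 35%: q, expected, chance |
|---|---|---|
| 0% | 0, 0, 0 | 0, 0, 0 |
| 25% | 0.05, 0.75, 0.54 | 0.0875, 1.31, 0.75 |
| 50% | 0.10, 1.50, 0.79 | 0.175, 2.63, 0.94 |
| 100% | 0.20, 3.00, 0.965 | 0.35, 5.25, 0.998 |

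The counts use 15, not 17. The extra two subjects allow for non-evaluability, and under Section 9.2.2 a subject with a response after the Cycle 1 treatment days is evaluable.

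**4. Effect on the median.** With r responders (CR or CRi) of 15, at least 15 − r subjects fail on day 0 under either rule. If r ≤ 7, that is at least 8/15 = 53.3%, so median EFS is zero under both. P(r ≤ 7) is 88.7% at a 35% rate, which is the last entry of Table 5. At 20% it is 99.6%. The medians can differ only when 8 or more respond, which has probability 100 − 88.7 = 11.3% at 35%.

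**5. Is the text inconsistent?** Four places bear on whether CR in the EFS bullet might mean both categories:

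- Section 9.2.1 gives CRi its own definition, and a subject with residual cytopenia does not meet the CR counts.
- Footnote k of the Time and Events Schedule and Section 9.2.1 (Bone Marrow Examination) call for a marrow at the end of Cycle 2 when CR has not been reached. CR is therefore the higher bar there too.
- The bullets just above EFS in Section 9.2.2 write CRi out when it is meant.
- Only the shared introduction in Section 9.2.1 groups the two.

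The weight of usage favours the narrow reading, under which the EFS rule is complete and can be applied without guessing. A subject whose CRi later becomes CR is not affected.

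**The case for a change.** The strongest case for a change is that CRi-only responders are likely in this trial. Both drugs suppress the marrow. Section 3.2 reports slower platelet recovery after DACOGEN priming in a paediatric study. Section 10.2 stops treatment once a response is good enough for transplant, and Section 9.2.1 ends efficacy evaluations at transplant, so a child could leave in CRi before counts recover. The protocol gives no reason for a stricter bar in EFS than in the primary endpoint. The clause on alternatives names none and sets no deadline. The remedy would be a sentence and one table.

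Much of this stands as description: such subjects are plausible, and each one moves the early curve. It does not make the rule wrong. A secondary endpoint may use a stricter standard than the primary, and an unstated rationale is not an error. The clause on alternatives follows a fully stated definition and reads naturally as allowing additions beside it; nothing lets the stated version be dropped. Whether alternatives are named in the Statistical Analysis Plan cannot be judged from the documents at hand. The low cost of the remedy matches its low yield: the dates of CR, CRi and relapse are already collected, so a CR + CRi version can be produced at any time as a supplementary table.

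**Conclusion.** No change to the plan is needed. As written, EFS is a CR-only measure. It is stricter than the primary endpoint, internally coherent, and reported without a hypothesis test; Section 2.1 even places it among the other objectives. The mismatch costs 6.7 points of the curve just after day 0 per CRi-only responder (5.9 on 17 subjects), and shows in the early curve and landmark rates. It leaves the primary CR + CRi rate, Table 5 and the sample size as they are. The median is zero under both definitions with probability 88.7% at a 35% response rate and 99.6% at 20%, taking 15 evaluable subjects and the binomial model that Table 5 uses. The number of subjects affected rests on an assumed CRi-only share, which the documents do not give.

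What remains is a detail that analysts can settle sensibly: confirm in the Statistical Analysis Plan that EFS is CR-only, and list any CR + CRi version there as supplementary. That is optional, and no conclusion of the trial depends on it.
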